### 1.5 Additional (Secondary) analyses of the primary Aim 1.

**1.5.1 Intention to treat and as-treated analyses.** In secondary analyses, we will perform both "as treated" and "intention-to-treat" analyses. In the as-treated analysis, patients who received one of the study medications will be included in the statistical analysis in the treatment group corresponding to the treatment that they actually received. In the "intention-to-treat", patients will be included in the statistical analysis in the treatment group corresponding to the treatment to which they were randomized. The intention to treat analysis will include all randomized patients with a few exceptions (see sections 1.3 or 1.4 above). These analyses will be conducted in a manner similar to the per-protocol analysis, but including different patients and different follow-up time.

**1.5.2. Analyses aggregating those on either rivaroxaban or warfarin.** As an additional secondary analysis, we will also perform a pair-wise comparison of aspirin vs. an aggregate of patients who received either rivaroxaban or warfarin. In this analysis, we will pool the data from those who receive either rivaroxaban or warfarin. This analysis will be based on only those patients eligible for aspirin and either rivaroxaban or warfarin.

**1.5.3 Analyses based on different time periods.** In an additional secondary analysis, we will compare the treatment groups with respect to risk of events in the first 7 days post-surgery, and in the first month post-surgery.

**1.5.4 Analyses adjusting for potential confounding created by exclusion of some patients, loss to follow-up, or switching from randomized treatment.** Inevitably there will be some randomized patients who are lost to follow-up at one time or another. These patients will be censored at the time they were lost to follow-up. In addition, as mentioned above, we will censor patients when they switch from the treatment to which they were randomized, and exclude those who do not have surgery or have events before surgery. The missing or excluded data can result in imbalances between

the groups that can confound comparisons. Therefore, in a secondary analysis, we will adjust for these imbalances using weights. Specifically, we will calculate an adjusted Kaplan-Meier estimate using the method described by Xie and Liu (2005, *Statistics in Medicine* 24:3089:3110). This is an approach that involves weighting each observation by the inverse probability of being in one group (vs. the other group) when calculating the Kaplan-Meier estimates. Candidate variables for weighting will include age, sex, site, date of surgery, and education. Weights will be derived so that, after weighting each participant, the groups will be comparable with respect to the proportion of follow-up in each subgroup defined by the covariates. This will effectively remove confounding due to imbalances between the groups with respect to these measured covariates. These adjusted Kaplan-Meier estimates can be calculated in SAS 9.4.

This approach will result in unbiased estimates if the data are “missing at random” (i.e., missingness may depend on observed patient characteristics but not on the outcome). To address the possibility that the data are “missing not at random” we will perform some sensitivity analyses. One sensitivity analysis will be to perform an intention-to-treat analysis after excluding the sites with the greatest cross-over rates. Another would be to assess impact of various degrees of departure from the missing-at-random assumption on the qualitative conclusions using methods described by [name] LS. (*Control Clin Trials*. 2003 Aug;24(4):411-21) or by Kim et al (Kim M, Wang C, Xue X. (2019) *Stat Med* 38:650-659). However, these methods are designed for binary data and will have to be adapted to time-to-event data that we will use as our outcome.

**2.0 Primary Aim 2.** *To compare the frequency and nature of bleeding complications (major, clinically important, and wound-related bleeding) leading to persistent wound drainage, reoperation, deep infection, or myocardial infarction.*

Using the same methods as described for Aim 1, 6-month probabilities of our primary composite safety endpoint inclusive of bleeding complications by treatment group will be estimated and compared. The primary analysis will be a per-protocol analysis for as described above for Aim 1. Sensitivity analyses for missing outcomes will be performed as described above for Aim 1.

**3.0 Primary Aim 3.** *To compare patient-reported outcomes (PRO) in patients experiencing primary effectiveness and safety endpoints in order to assess the impact of such events on specific function of the replaced joint as well as general patient well-being.*

**3.1 Analysis Plan.** The primary patient-reported outcomes will be the HOOS, JR. (hip disability and osteoarthritis outcome score), the KOOS, JR. (Knee injury and osteoarthritis outcome score) and the PROMIS-10 measure of global health. The questions needed to calculate these scores will be asked at each time point (baseline, 1 month, 3 months and 6 months after surgery). These measures will be scored as recommended by the developers. The treatment groups will be compared with respect to the distribution of these scores at each time point. Formal inference regarding the impact of treatment on the changes in these scores will be performed using a general linear model. This will be fit using an unstructured covariance structure to allow a different variance at each time point and different covariances between each pair of time points. The model will include terms representing the mean outcome at each treatment/time/eligibility stratum combination.

In addition, we will compare the treatment groups with respect to specific items used to compute the HOOS, JR and KOOS, JR. For the KOOS, JR, we pre-specify interest in comparing the groups with respect to the following three questions:

1. How severe is knee stiffness after first waking in the morning?
2. What is the degree of difficulty when rising from sitting?
3. What is the degree of difficulty when bending to floor to pick up object?

For the HOOS, JR we pre-specify interest in the following two questions:

1. What is the degree of difficulty when rising from sitting?
2. What is the degree of difficulty when bending to floor to pick up object?

To assess the association between thromboembolic or bleeding complications and patient reported outcomes of function, pain, or quality of life, we will use models similar to those described above. We will add terms to the models representing the experience of a previous thromboembolic or bleeding complication.

As for Aims 1 and 2, the primary analysis will be based on the per-protocol follow-up with secondary analyses based on the intention-to-treat approach and the as-treated approach.

**3.2 Scoring the HOOS, JR or KOOS, JR when one or more items in the questionnaire are missing.** Patients who complete less than 75% of the HOOS or KOOS questionnaires will be excluded from this analysis. For those who completed 75% or more of the survey questions, missing responses will be imputed using EM (Expectation-Maximization) imputation.

The FORCE study has data on thousands of complete HOOS, JR and KOOS, JR assessments. This information can alternatively be used to develop models for imputing missing items as may be needed. Therefore, unidentified HOOS/KOOS data from our study will be sent to the FORCE team who will perform multiple imputation to result in multiple complete data sets. These data sets will be returned to the statistical coordinating center (UMB) for appropriate analyses of multiple imputation data.

**3.3 Addressing the problem of missing PRO data at some follow-up time points.** Because the proposed analysis is a likelihood-based analysis, the proposed analyses will be valid if the probability that a patient's PRO is missing at a given time point is at random given observed values of PRO's at other time points. If the probability of missingness is also dependent on other patient characteristics, (e.g., sex, age), these can be included in the model to provide unbiased estimates under the assumption that the probability of missingness is random given observed PRO's and these patient characteristics.

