In secondary analyses, we will also perform an intention to treat analysis and an “as-treated” analysis. In the intention to treat analysis, patients will be included in the analysis in the group to which they were randomized and only be censored when they are lost to follow-up. However, some patients who are randomized will be excluded from all analyses (See sections 1.3 and 1.4 below). In the “as treated” analysis, patients will be included in the group based on the study medication they actually received. Thus, for example, if a patient is randomized to rivaroxaban but receives aspirin, they will be included in the aspirin group. This approach will include “crossover” patients and provide more precise estimates of what actually happened to patients who took the study medications, but will need to be interpreted with caution as this approach has more potential to result in a lack of representativeness of the groups.

**1.2 Treatment Comparisons.** Next, each pairwise comparison of the treatment groups (i.e., aspirin vs. rivaroxaban, aspirin vs. warfarin, rivaroxaban vs. warfarin) will be performed separately, only including those patients with no medical contra-indication for either of the two treatments in that pair. In addition, for each pairwise comparison, we will only include those patients who were randomized at sites during a period of time where patients could have been randomized to either of the two treatments being compared. For example, a patient randomized to aspirin at a site restricted to use of rivaroxaban and aspirin cannot be included in an aspirin to warfarin comparison because that patient could not have received warfarin at their respective site (see below).

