**Table 1. Numbers of patients and resulting power and precision in comparing aspirin to warfarin.**

	Aspirin	Warfarin
Number Randomized as of May 1, 2023	5132	5389
Number Eligible for both treatments (either medically or due to logistics)	4703	4698
Projected number who took the assigned treatment 	4402	3688
Projected number who will have complete follow-up 	3962	3319
Projected width of the 95% CI for the difference in risk of primary outcome	0.96 percentage pts	
Power to obtain evidence of non-inferiority based on 0.69% margin of inferiority	80.3%	
Margin of inferiority detectable with 80% power	0.69 percentage pts	

Based on a crossover rate of 21.5% and 6.4% for Warfarin and Aspirin, respectively.

Assuming that 90% of those randomized have surgery, do not withdraw, and have 6-month follow-up information.

**Recruitment and randomization.** To achieve the total of approximately 18,000 evaluable patients we will recruit approximately 20,000 to accommodate the possibility of 10% loss to follow-up. We will randomize patients with equal probabilities to each of the three regimens using a web-based program provided by Statix. Those sites that are on the restricted randomization plan due to structural barriers will randomize patients using a 1:1 randomization scheme. Following removal of warfarin from the protocol in June 2023, all sites will randomize patients using a 1:1 scheme to either aspirin or rivaroxaban. The web application is available 24/7, password protected, and maintains an audit trail of transactions with time stamp login for users. There will be a separate randomization schedule for each clinical site, stratified according to operation (hip or knee) to ensure balanced intervention groups with respect to site and operation. Within each stratum, assignments will be randomly permuted within repeating blocks of varying size.

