A concealed centralized randomization schedule will provide assignment to one of the prophylaxis regimens, as specified in section 3.1.2b, in randomly varying block sizes of 3, 6, and 9 developed separately for each clinical site and stratified according to type of surgery (hip or knee replacement).

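### The secondary analysis in section 1.5.2 pools rivaroxaban and warfarin across 1:2 and 1:1 allocation strata without stratifying, so it can be confounded by site and era; block sizes 3 and 9 in section 4.1.1 do not fit a two-arm 1:1 scheme

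*Protocol*

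**What the plan says.** **Pooled analysis.** Protocol section 1.5.2 sets the data to be used: "In this analysis, we will pool the data from those who receive either rivaroxaban or warfarin". It sets the population by eligibility: "This analysis will be based on only those patients eligible for aspirin and either rivaroxaban or warfarin". The either/or wording admits patients who had only one of the two comparators open to them. No stratification, weighting or margin is stated for this analysis.

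**Allocation.** The recruitment and randomization paragraph after Table 1 describes three settings:
- Three arms: "We will randomize patients with equal probabilities to each of the three regimens using a web-based program provided by Statix".
- Restricted sites: "Those sites that are on the restricted randomization plan due to structural barriers will randomize patients using a 1:1 randomization scheme".
- After the change: "Following removal of warfarin from the protocol in June 2023, all sites will randomize patients using a 1:1 scheme to either aspirin or rivaroxaban".

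**Method.** Section 1.2 compares two groups by the difference of their Kaplan-Meier risks with Greenwood variances. Each pairwise comparison is limited to patients "randomized at sites during a period of time where patients could have been randomized to either of the two treatments being compared". Section 1.5.4 offers inverse-probability-weighted Kaplan-Meier estimates as a secondary analysis, motivated by exclusions, loss to follow-up and switching. Site and date of surgery are candidate variables there. Section 1.2, which points to the same weighting, lists site but not date of surgery.

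**Blocks.** Section 4.1.1 describes the schedule as "in randomly varying block sizes of 3, 6, and 9 developed separately for each clinical site". Section 3.1.2(d) describes two groups, aspirin and rivaroxaban, with varying block sizes and no numbers. Section 4.1.1 also keeps stratified randomisation for patients with a contraindication to one or two of three regimens, whereas section 3.1.2(d) makes a contraindication to one of the two regimens exclusionary.

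**The concern.** When the allocation ratio differs between strata, the crude groups contain the strata in different proportions. Within each stratum the comparison is randomised; after simple pooling it no longer is. Two-arm strata (restricted sites, patients with a contraindication before the change, everyone after it) are over-represented in the aspirin group. If risk in those strata differs, aspirin looks better or worse than the pooled comparator even when the drugs are identical.

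A difference in risk is plausible on the protocol's own account. Enrolment runs over 97 months and across the pandemic, the protocol cites a link between Covid and thromboembolism, and the restricted sites are restricted for structural reasons.

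The block-size text is a smaller, separate matter. A list built from blocks of 3 or 9 cannot allocate two arms equally within a block, and naming sizes in an open-label trial with site-level lists gives away information for no benefit.

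**Working it through.** **1. The plan's own figures.** The protocol gives no figure for 1.5.2. The nearest is Table 1 (aspirin versus warfarin), and it reproduces:
- Counts: 4703 × 0.936 = 4402 and 4698 × 0.785 = 3688; times 0.9 gives 3962 and 3319.
- SE = √[0.011 × 0.989 × (1/3962 + 1/3319)] = 0.00245.
- CI width = 2 × 1.96 × SE = 0.96 points (stated 0.96).
- Power = Φ(0.0069/SE − 1.96) = 80.3% (stated 80.3%).

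**2. Inputs for the pooled contrast.**
- Projected totals (section 5.1): aspirin 7239, rivaroxaban 7223, warfarin 5389.
- Eligible for both aspirin and warfarin (Table 1): aspirin 4703, warfarin 4698. These stand in for the three-arm strata.
- Assumption: rivaroxaban equals aspirin within each stratum, so 4703 in three-arm and 7239 − 4703 = 2536 in two-arm strata.

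**3. Stratum mix.**
- Ratio in three-arm strata: (4698 + 4703)/4703 = 2.0. In two-arm strata: 2536/2536 = 1.0.
- Aspirin from two-arm strata: 2536/7239 = 35.0%.
- Pooled comparator from two-arm strata: 2536/(4698 + 4703 + 2536) = 2536/11,937 = 21.2%.
- Gap: 13.8 percentage points.

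**4. Spurious difference with identical drug effects.**
Bias = (two-arm share in aspirin − two-arm share in comparator) × (two-arm risk − three-arm risk) = 0.138 × risk gap.

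| Assumed risk gap (points) | Spurious difference (points) |
|---|---|
| 0 | 0 |
| 0.2 | 0.03 |
| 0.8 | 0.11 |

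The sign follows the gap: higher risk in two-arm strata counts against aspirin, lower risk in its favour. The risk gaps are assumptions; the protocol gives none.

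**5. Sensitivity to the counts.** Splitting by calendar period alone, with 5132 aspirin patients randomised by 1 May 2023 and the same number assumed for rivaroxaban: 5132/7239 = 70.9% of aspirin against (5389 + 5132)/12,612 = 83.4% of comparators, a gap of 12.5 points. Varying the pre-change rivaroxaban count from 4700 to 5400 gives 9.1 to 14.7 points.

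**6. Do the existing rules remove it?** The concurrency rule drops patients who could not have received a compared treatment. At a two-arm site both aspirin and one member of the aggregate were available, so those patients stay, and the ratio still changes from 1:2 to 1:1. The section 1.5.4 weights could remove the term, but only if site and date of surgery are actually used and the weighting is applied to 1.5.2; neither is stated.

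**7. Blocks.** 6 divides by 2; 3 and 9 do not. All three divide by 3, so the list fits the three-arm design.

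**The case against.** The strongest case against has four parts.

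*It is one secondary analysis, with tools at hand.* Section 1.5.2 calls itself a pairwise comparison, so it may inherit the concurrency rule, and 1.5.4 supplies a suitable weighting method. An analysis plan not shown here may stratify. What stands: concurrency does not equalise the ratio, the weights are optional and aimed at another problem, and 1.5.2 already fixes the pooling and the population.

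*The size is uncertain and modest.* This stands. By their labels, 7239 counts patients assigned and treated over the whole trial, while 4703 counts eligible randomised patients at May 2023 and may include some who could not receive rivaroxaban. At 1.1% risk, the 95% half-width for 7239 versus 11,937 patients is 1.96 × √[0.011 × 0.989 × (1/7239 + 1/11,937)] = 0.30 points, larger than the 0.03 to 0.11 above. Expressing the bias as a share of the 0.69-point margin would borrow a margin that 1.5.2 does not set.

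*The two-arm change was made.* A reader might infer from section 4.1.1 that it was generally not carried through. The documents do not support that: the opening of 3.1.2, section 3.1.2(d) and the randomization paragraph after Table 1 all make it. The leftovers in randomisation are in 4.1.1.

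*Blocks and concealment.* A reader might infer that none of the listed sizes works, or that assignments can be guessed at some calculable rate. A block of 6 balances two arms. Guess rates would need known block boundaries and an assumption about how warfarin slots were handled; the protocol describes a concealed central schedule with randomly varying sizes and says nothing of skipped slots. Nothing shows that blocks of 3 or 9 are used on two-arm lists.

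**Conclusion.** The point holds for the pooled contrast in 1.5.2. As written, it merges 1:2 and 1:1 strata in a crude comparison and can be confounded by site and era. The likely size is about 0.14 times the risk gap between strata: 0.03 to 0.11 percentage points for an assumed gap of 0.2 to 0.8, and nothing if risk does not differ. This rests on approximate counts and on equal aspirin and rivaroxaban numbers within strata.

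A reader might go further and infer that the main non-inferiority result is biased. It is not, by this mechanism: aspirin versus rivaroxaban is 1:1 in both settings. Nor do the documents show that 1.5.2 *is* confounded, only that it is unprotected.

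The block sizes in 4.1.1 contradict the two-arm 1:1 scheme for 3 and 9, and the contraindication text in 4.1.1 conflicts with 3.1.2(d). Both are text corrections.

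**What to change.** **Section 1.5.2.** Choose one:
1. Estimate the risk difference within randomisation scheme (three-arm or two-arm, ideally also by site and period) and combine with Mantel-Haenszel or inverse-variance weights. With fine strata and events near 1%, Mantel-Haenszel weights are safer, because strata without events break inverse-variance weights.
2. Apply the section 1.5.4 weighting to this analysis with site and date of surgery mandatory.
3. Limit it to patients randomised while all three arms were open to them.

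On the counts above at 1.1% risk, two-stratum inverse-variance weighting has variance factor 1/[1/(1/4703 + 1/9401) + 1/(2/2536)] = 0.000227, against 0.000222 crude, so the half-width goes from 0.305 to 0.308 points. Option 3 has factor 1/4703 + 1/9401 = 0.000319 and a half-width of 0.37, so it is simple but about 20% less precise.

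**Section 4.1.1.** Replace the listed block sizes with even, varying sizes that the protocol does not disclose, and reconcile the three-regimen contraindication text with section 3.1.2(d).

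The cost is a few protocol sentences and a little analysis code.

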## **4.0 Secondary Aims Data Analysis**

**4.1 Secondary Aim 1 Analysis (a):** *Analysis of the contribution of "standard of care" methods of anesthesia (general vs regional neuraxial anesthesia) on clinical effectiveness of three different prophylaxis regimens.* To address this aim, we will compare those with general to those with regional anesthesia with respect to risk of the clinical and patient-reported outcomes, overall, and in strata defined by treatment. To assess whether the impact of treatment on outcomes varies by anesthesia type, we will fit longitudinal regression models with interaction terms between treatment and anesthesia type. These models will include random effects for patient and surgeon to account for correlation between repeated measures on the same patient and surgeon. For the binary events in time (e.g., our primary composite outcome for Aim 1), this will be assessed using a Cox regression model with an identity link, censoring patients at the time of loss to follow-up or treatment switch. The interaction terms in this model will represent the difference in the treatment group risk differences between those on general and those on regional anesthesia. The p-values for these terms will provide a measure of the strength of evidence of a difference in treatment effect by anesthesia. We will also adjust for covariates such as age, baseline comorbidities, and surgery type by including them in the model if they appear to confound the relationship between anesthesia and outcomes. Standard errors of estimates in the model will be calculated using a robust variance estimate to account for the clustering within patients and surgeons. We are accounting for clustering by surgeon in the analysis because anesthesia methods may vary by surgeon, so we need to adjust for surgeon.

**4.2 Secondary Aim 2 Analysis (b)** *Analysis of the relative frequency of thromboembolic events and bleeding complications between hip and knee replacement patients with each of the three regimens.* We will use the methods described above for Aims 1-3 separately for knee and hip patients. Formal assessment of whether event rates or the impact of the treatments differ between those provided knee or hip replacement will be performed using Cox regression with interaction terms between treatment and operation type.

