## 3.1.3. Data Analysis

Primary Data Analysis

The unblinded nature of the clinical trial could threaten unbiased comparisons. Randomized patients will not be notified of treatment group assignment until the day of the proposed operation, unless necessary to provide third party insurance coverage for prescribed medical care. Further, our trial is protected from this threat to adherence with treatment assignment by the short course of treatment, the follow-up contact to ascertain treatment, and the motivation of each patient to take prescribed drugs to prevent PE and DVT. The trial is protected from the threat to unbiased outcome ascertainment and classification by the independent centralized contact with patients to determine need for collection of clinical documents, preparation of documents related to readmission or treatment for bleeding or thrombosis to remove any indication of treatment assignment, and blinded outcome classification based upon expert review of the redacted documents by the OAC.

**1.0 Primary Aim 1.** *To compare the frequency of the aggregate clinical endpoint of important venous thromboembolism (clinical PE and DVT leading to hospital readmission) and all-cause mortality.*

**1.1 Risk Estimates.** First, 6-month probabilities of our primary composite endpoint (clinical PE, clinical DVT, and all-cause mortality) by treatment group will be estimated and compared. To address the fact that some participants will have incomplete follow-up (e.g., we may know whether they had an event within 3 months but not for the full 6 months), we will estimate 6-month risk of an event using a Kaplan-Meier approach. Confidence intervals will be based on Greenwood's formula (applied using the delta method to a complementary log-log transformation of the estimated risk). In these calculations, those whose follow-up is incomplete will be censored at the time that the follow-up ends.

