For each pairwise comparison we will calculate a two-sided 95% confidence interval for the risk difference (i.e., the difference between the groups with respect to risk of the composite endpoint) based on the variances of each estimated 6-month risk calculated by Greenwood’s formula. These confidence intervals will be interpretable as the range of differences that cannot be ruled out by a test at the two-sided 5% level. Next, the strength of evidence for non-inferiority of aspirin relative to rivaroxaban with respect to risk of our primary endpoint will be formally assessed by calculating a one-sided p-value for the null hypothesis that the 6-month risk of an event among those in the aspirin group is at least 0.69 percentage points greater than the risk among patients taking rivaroxaban. A low p-value indicates evidence against this hypothesis and would suggest that the risk among those taking aspirin is less than 0.69 percentage points greater than the risk among those taking rivaroxaban. The p-value will be based on the test statistic:

$$= \frac{\hat{r}_{\text{aspirin}} - \hat{r}_{\text{rivaroxaban}} - 0.0069}{\sqrt{\text{VAR}(\hat{r}_{\text{aspirin}}) + \text{VAR}(\hat{r}_{\text{rivaroxaban}})}}$$

where  $\hat{r}_{\text{aspirin}}$  is the estimated risk of events in the aspirin group and  $\hat{r}_{\text{rivaroxaban}}$  is the estimated risk in the rivaroxaban group. The p-value will be the probability that a standard normal random variable will be less than this value. Note, a one-sided test (rather than a two-sided test) is appropriate for evaluation of a non-inferiority hypothesis and is recommended by Farrington and Manning. An analogous statistic will be calculated to compare aspirin to warfarin.

The standard analysis for superiority trials is to base the analysis on the principle of intention to treat. In this analysis, patients are included in the group to which they were randomized, irrespective of the treatment actually received. However, as recognized by the FDA in their guidance, in a non-inferiority analysis, the intention-to-treat analysis is biased towards finding non-inferiority because protocol violations and cross-overs tend to diminish

 <https://www.fda.gov/downloads/Drugs/Guidances/UCM202140.pdf>

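### Section 4.1 gives its identity-link Cox interaction a risk-difference meaning it does not have, and section 4.2's formal hip/knee interaction test is by default on a different scale from the trial's 6-month risk difference

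*Protocol*

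**What the plan says.** All references are to the protocol, section 3.1.3 Data Analysis; the statistical analysis plan was not available.

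- **Primary scale (1.1 and 1.2).** The basic quantity is the 6-month risk: "we will estimate 6-month risk of an event using a Kaplan-Meier approach". Treatments are compared by absolute difference: "For each pairwise comparison we will calculate a two-sided 95% confidence interval for the risk difference". The non-inferiority null hypothesis is on the same scale, with aspirin's risk "at least 0.69 percentage points greater than the risk among patients taking rivaroxaban".
- **Anesthesia (4.1).** For the time-to-event outcomes, "this will be assessed using a Cox regression model with an identity link", with censoring at loss to follow-up or treatment switch. The next sentence interprets the result: "The interaction terms in this model will represent the difference in the treatment group risk differences" between general and regional anesthesia. Covariate adjustment and a robust variance for clustering by surgeon are planned.
- **Hip versus knee (4.2).** The Aim 1 to 3 methods are first applied to knee and hip patients separately. The formal assessment of whether event rates or treatment effects differ by joint then "will be performed using Cox regression with interaction terms between treatment and operation type". No link or effect scale is given.

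**The concern.** There are two linked problems.

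First, 4.1 attaches to its model a meaning the model does not have. An identity link on the hazard gives an additive-hazards model, whose coefficient is a difference in event rate per unit of time. Turning that into a difference in 6-month risk needs a further step over the 180 days, and the protocol describes none. (Read instead as a linear form of the relative hazard, the coefficient would be an excess hazard ratio, which is further still from a risk difference.)

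Second, 4.2 tests the same kind of question with ordinary Cox regression, whose interaction is a ratio of hazard ratios. Two sibling tests of effect modification therefore sit on different scales, and the one in 4.2 matches neither the target declared in 4.1 nor the primary analysis.

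At stake is how effect modification is reported. If hip and knee patients differ in baseline risk, a constant hazard ratio implies different absolute differences. A null Cox interaction could then be read as saying that the treatment effect is the same in both joints when, on the trial's own scale, it is not.

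**Working it through.** **1. Confirm the planning scale.** Table 1 gives 3962 aspirin and 3319 warfarin patients with complete follow-up; section 5.2 gives a risk of 1.1%; the margin is 0.69 points.

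- SE = sqrt(0.011 × 0.989 × (1/3962 + 1/3319)) = 0.245 points.
- Width of the 95% interval = 2 × 1.96 × 0.245 = 0.96 points (stated: 0.96).
- Power = Φ(0.69/0.245 − 1.96) = 80.3% (stated: 80.3%), at one-sided 0.025.

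The plan's figures reproduce, so its design scale is the absolute 6-month risk difference.

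**2. Section 4.1: hazard difference against risk difference at low risk.** With risk = 1 − exp(−cumulative hazard), a cumulative-hazard difference of 0.69 points on a baseline risk of 1.1% gives a risk difference of 0.989 × (1 − exp(−0.0069)) = 0.680 points. At assumed baseline risks of 0.6% and 1.6% the values are 0.683 and 0.677, a spurious interaction of about 0.007 points. This part of the gap is negligible.

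**3. Section 4.1: early effect with later censoring.** A constant-coefficient additive model averages the hazard difference over the time at risk. Prophylaxis lasts 30 days and the endpoint runs to 6 months, so an early excess is plausible. Assume a cumulative hazard of 0.012 vs 0.006 over days 0 to 30, no difference afterwards, and uniform censoring over days 30 to 180.

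- True risk difference: exp(−0.006) − exp(−0.012) = 0.595 points.
- Coefficient × 180 days ≈ 0.600 / (average proportion still at risk).

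| Censored by day 180 | Average proportion at risk | Coefficient × 180 (points) |
|---|---|---|
| 0% | 1 | 0.600 |
| 10% | (30 + 150 × 0.95)/180 = 0.958 | 0.626 |
| 25% | (30 + 150 × 0.875)/180 = 0.896 | 0.670 |

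The protocol assumes 10% for no surgery, withdrawal and loss combined, so the 10% row is the relevant one: a gap of about 0.03 points. The 25% row has no support in the protocol and only shows the range. The calculation is for a treatment effect, not for an interaction.

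**4. Section 4.2: hazard-ratio scale against risk-difference scale.** The protocol gives no risks by joint, so these are assumptions.

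| | Risk, aspirin vs comparator | Hazard ratio | Risk difference |
|---|---|---|---|
| Hip | 1.05% vs 0.70% | ln(0.9895)/ln(0.9930) = 1.503 | 0.35 points |
| Knee | 2.10% vs 1.40% | ln(0.9790)/ln(0.9860) = 1.505 | 0.70 points |

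The Cox interaction is essentially null while the risk difference doubles. Likewise, the hazard ratio equivalent to the margin at 1.1% is ln(1 − 0.0179)/ln(1 − 0.011) = 1.63. Held constant, it gives risk differences of 0.38 points at a baseline of 0.6% and 1.00 points at 1.6%.

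**5. Precision of a risk-difference contrast, hip versus knee.** Take one third hip and two thirds knee (planned enrollment table), risk 1.1%, and group sizes implied by the margins of error in section 5.2: 1.96² × 0.011 × 0.989 / 0.0027² ≈ 5733 for aspirin and, with 0.0030, ≈ 4644 for rivaroxaban.

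SE = sqrt(0.011 × 0.989 × (3/5733 + 3/4644 + 1.5/5733 + 1.5/4644)) = 0.44 points, a 95% half-width of 0.86.

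With 90% of the 7239 and 7223 projected in section 5.1, the SE is 0.39.

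**The case against.** A reader might infer that these analyses leave the trial unable to show whether aspirin's non-inferiority at 0.69 points holds in each joint. The protocol does not support that. Section 4.2 opens by repeating the Aim 1 methods separately in hip and knee patients, which brings in the Kaplan-Meier risk difference, its interval and the margin test. In the illustration, the knee difference of 0.70 would be reported directly, whatever the Cox interaction showed.

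Nor does either section say that its interaction test decides the margin question. Section 3.1.4 (Data Sharing) separately plans to look at risks in subgroups for non-inferiority, and secondary aim (b) is framed as relative frequency, for which a ratio-scale test can be defended.

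A reader might also infer that the 4.1 results would be seriously distorted. They would not. Its declared target is the risk difference, the low-risk approximation is good, and the early-excess gap is small. With similar timing and censoring under both anesthesia types, most of that gap would cancel in the interaction. Rescaling by a constant also leaves the interaction p-value unchanged.

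Finally, details of a secondary model are often left to the statistical analysis plan. That covers an omitted link in 4.2 to some extent. It does not cover 4.1, where the protocol names a model and states an incorrect meaning for its coefficient. The two sections also remain on different scales as written.

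**Conclusion.** The point holds, with limited scope. Section 4.1 misstates what its named model estimates; the numerical consequence is about 0.03 points under the assumed early-excess scenario with 10% loss. The formal interaction test in 4.2, read as default Cox regression, is on the hazard-ratio scale. It can be null when absolute risk differences clearly differ, 0.35 against 0.70 points in an illustration that rests on assumed risks by joint. If baseline risks were similar in hip and knee, the two scales would largely agree.

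Only the secondary aims are affected. The primary comparison, the margin and the sample size do not change. Severity is minor to moderate.

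**What to change.** 1. In 4.1 and 4.2, define the formal interaction test as the difference between stratum-specific 6-month Kaplan-Meier risk differences: z = (RD1 − RD2) / sqrt(sum of the four Greenwood variances), reported with its 95% interval.
2. For the covariate-adjusted analysis in 4.1, regress 6-month pseudo-values on treatment, anesthesia type, their interaction and the covariates, with an identity link and a robust variance clustered by surgeon. The interaction coefficient then has the meaning that 4.1 intends.
3. Delete the identity-link Cox wording, or correct its interpretation to a difference in hazards.
4. Keep the Cox hazard-ratio interaction as a supportive analysis, labeled as such.

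This takes a few sentences and, for hip versus knee, reuses estimates already planned. The downside is precision. With an SE of about 0.44 points (0.39 under the larger assumed group sizes), a contrast of 0.35 points, as in the illustration, would not be distinguishable from zero. The result should therefore be presented as an estimate with its interval, and a non-significant test should not be read as evidence of a uniform effect.
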